Eligible subjects will have controlled HIV infection and a diagnosis of mild to moderate COPD and/or based on established criteria. Subjects will be randomized by the research pharmacist in a 2:1 fashion using permuted blocks of size 3 to receive doxycycline or placebo for 6 months and will undergo serial measures of lung function by spirometry as well as bronchoscopies at baseline and week 12 to collect specimens for translational studies aimed at characterizing the biological effects of the intervention. The bronchoscopy will be performed mainly as an outpatient procedure. The investigator may stop the procedure at any time if he/she feels that sufficient samples have been collected and/or it is not safe to continue the procedure. Subjects are expected to have an escort on the day of the bronchoscopy in order to undergo the bronchoscopy procedure. If the escort does not arrive or if no responsible adult is available to escort the subject home once the bronchoscopy procedure is complete, the subject will undergo observation by research staff until deemed stable. Follow-up calls will be performed one day (+/-3 days) and one week (+/-3 days) post-bronchoscopy. The randomization will be stratified on current versus former smoking status. The study is double-blinded, and only the research pharmacist will have knowledge of the treatment assignments, which is needed to dispense the study drug. Despite the pilot nature of this study, we have opted to conduct a randomized, placebo-controlled trial primarily to ensure that there is a control group to be able to interpret changes in biologic and physiologic endpoints that may vary based on the natural variation in the course of COPD and/or variability in the assays/assessments. We will randomize 2:1 in favor of active study drug to enable us to have a sufficient number of recipients of active drug within the constraints of a small study.

**Number of subjects (planned):** 30 subjects will be enrolled and will be randomized in a 2:1 fashion. Subjects for this study will be recruited from the referral base of the investigators from the population of individuals with COPD and documented HIV as defined by the protocol inclusion/exclusion criteria (see below).

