Data will be entered into the REDCap, a PHP-based system developed by Vanderbilt University and currently managed and updated through a national consortium that includes the Weill Cornell CTSC. In collaboration with the CTSC's data management group, we will create a secure, HIPAA-compliant, web-based study-specific database system with customized full field validation capabilities, a full audit trail and user-based privileges.

We will compute summary statistics (e.g. mean, median, SD, interquartile range, minimum and maximum) for demographic/clinical variables and the primary outcome data (e.g. spirometry endpoints, adverse events, biological endpoints, measurable doxycycline levels in serum and

ELF) by study arm. We will compare changes from baseline in continuous variables between the two groups by 2-sample t-tests or the non-parametric Wilcoxon's rank sum test as appropriate. We will perform repeated measures ANOVA or Multivariate ANOVA for repeated measures data (e.g. spirometry) as deemed appropriate after checking assumptions of sphericity using Mauchly's Test. Given the moderate sample size for this data we will compute confidence interval for estimates from RMANOVA or MANOVA to assess their precision. The proportions of subjects in each arm experiencing adverse events will be summarized by grade and compared by Chi-squared or Fisher's exact tests or generalized Fisher's test (using Monte Carlo approximations) as appropriate. In a pre-specified subgroup analysis, we will explore whether the subset of subjects with emphysema by CT respond differently to doxycycline compared to those without emphysema.

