Research blood: Bronchoscopy visits (Week 0/Entry and Week 12), blood samples are collected for: doxycycline blood levels, EMP, DNA, serum (doxycycline assay, biomarker assay, DGM biobank), and monocytes. Non-bronchoscopy visits: (Week 2, Week 6, and Week 18 and Week 24) blood samples are collected for: doxycycline blood levels and serum for (doxycycline assay, biomarker assay and DGM biobank). Serum for biomarker assay will be frozen at -80°C for future assays (hsCRP, IL-6, TNF- $\alpha$ , IL-1 $\beta$ , procalcitonin). Should subject pre-maturely discontinue from the study, the subject will be invited to at least provide blood samples for the doxycycline blood assay.  Prostaglandin E urine collection, 9 mL. \*\*All subjects will be assessed for eligibility. PGE will be collected for any subject, who passes the screening as per the PI's recommendation, and has not taken NSAIDS within the past 7 days. Otherwise, subject will not be eligible for the PGE urine collection.

 Urine analysis will be collected to measure protein levels and kidney functions

 Urine metabolites will be collected to measure poisonous alkaloid from tobacco and the break-down product of nicotine from cigarette smoke

 Bronchoalveolar lavage;  $\geq$  50mL. To minimize any risk of bleeding to a subject after completion of the bronchoscopy procedure, subjects are advised not to take non-steroidal anti-inflammatory drugs (NSAIDs), such as aspirin and/or ibuprofen, for up to 7 days post-procedure.

 CT-scans taken within the last 6 months may be acceptable. Subjects will not be asked to complete more than 2 HRCT scans in one year If subjects complete the maximum of two HRCT scans in one year, they will receive no more than 2200mrem of radiation, which is within the guidelines for radiation exposure for human subjects; it is also below the maximum permissible dose limits per year for radiation workers according to the Nuclear Radiation Committee (5000mrem/year).

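### Minor: change-from-baseline tests use neither the baseline value nor the smoking stratum as a covariate, and so may give away precision at 20 versus 10

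*Combined protocol and SAP*

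**What the plan says.** The analysis of continuous endpoints is set out in one paragraph of the Synopsis, under Statistical Considerations: "We will compare changes from baseline in continuous variables between the two groups by 2-sample t-tests", with Wilcoxon's rank-sum test as the alternative. For endpoints measured several times it adds: "We will perform repeated measures ANOVA or Multivariate ANOVA for repeated measures data (e.g. spirometry) as deemed appropriate". Neither sentence names a covariate. ANCOVA, covariate adjustment and stratified analysis appear nowhere else in the document. The same paragraph shows an interest in precision: "Given the moderate sample size for this data we will compute confidence interval for estimates from RMANOVA or MANOVA to assess their precision".

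The Synopsis, Study Design, describes the allocation: 30 subjects, 2:1, permuted blocks of 3, and "The randomization will be stratified on current versus former smoking status".

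Baselines are scheduled for the endpoints at issue:
- Bronchoalveolar lavage (BAL): "bronchoscopies at baseline and week 12 to collect specimens for translational studies aimed at characterizing the biological effects of the intervention".
- Serum markers: footnote 5 of Table I (Section 7.2) has "Bronchoscopy visits (Week 0/Entry and Week 12), blood samples are collected for: doxycycline blood levels, EMP, DNA, serum (doxycycline assay, biomarker assay, DGM biobank".
- Spirometry and the CAT: both are marked at Entry in Table I.

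**The concern.** The design collects a baseline for most secondary endpoints and balances the arms on smoking, but the analysis uses the baseline only by subtracting it and does not use smoking at all. Subtraction fixes the slope on baseline at 1. When r is well below 1, that over-corrects and carries baseline noise into the estimate. Omitting a stratification factor that predicts change leaves its variation in the residual, so the standard error is too large for the balanced allocation that was achieved.

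This bears on a stated purpose of the trial. The Study Design text gives as the main reason for randomising against placebo "to ensure that there is a control group to be able to interpret changes in biologic and physiologic endpoints". That control group will have about 10 subjects, and the biologic results are meant to inform a larger trial. Precision that can be had from data already scheduled is worth taking.

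**Working it through.** **The plan's own figure.** The only power statement concerns toxicity: about 80% power, n = 20, true rate 20%, null rate 45.5%, one-sided 0.05. The exact binomial rule of rejecting at 5 or fewer events gives 80.4% power with alpha 0.0505, so it reproduces. It does not involve the continuous endpoints. For those the plan gives no power, SD, correlation or smoking effect, so r and the smoking effect below are assumed ranges.

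**Inputs from the documents.** 20 versus 10; two smoking strata; blocks of 3. The base case takes 15 current and 15 former smokers, split 10:5 within each stratum.

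**1. Variance.** With equal SD at both times and k = 1/20 + 1/10 = 0.15:
- change score: 2(1 − r) × SD² × k
- ANCOVA: (1 − r²) × SD² × k × (1 + 1/26), the last factor being the average cost of estimating the baseline slope
- ratio: (1 + r)/2 × 1.0385

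A stratum that is exactly balanced adds almost nothing to this factor and costs one degree of freedom.

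**2. Confidence interval width.** Multiply the square root of the ratio by t(26 df)/t(28 df) = 2.0555/2.0484 = 1.0035.

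| r | variance ratio | width, ANCOVA / change |
|---|---|---|
| 0.3 | 0.675 | 0.82 |
| 0.5 | 0.779 | 0.89 |
| 0.7 | 0.883 | 0.94 |
| 0.9 | 0.987 | 1.00 |
| 0.95 | 1.012 | 1.01 |

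Simulation (40,000 trials per cell) gives 0.824, 0.885, 0.942, 0.997 and 1.010. With permuted blocks of 3 in strata of random size (50% or 70% current smokers) the ratios are 0.82–0.83, 0.89, 0.94, 1.00 and 1.01.

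**3. Power.** The t-test on change (28 df) reaches 80% at a difference of 1.124 SD of change (noncentral t with noncentrality 1.124/√0.15 = 2.90). At that difference, simulated:

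| r | t-test | Wilcoxon (asymptotic) | ANCOVA |
|---|---|---|---|
| 0.3 | 80.4% | 76.3% | 92.5% |
| 0.5 | 80.2% | 75.8% | 88.6% |
| 0.7 | 80.3% | 76.3% | 84.6% |
| 0.9 | 79.7% | 75.6% | 80.0% |
| 0.95 | 80.2% | 76.1% | 79.4% |

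The exact Wilcoxon test gives 77–78%.

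**4. Source of the loss.** The standard error of the baseline difference between arms is √0.15 = 0.387 SD. An imbalance above 0.5 SD in either direction has probability 2 × [1 − Φ(0.5/0.387)] = 0.197 per endpoint. Given a 0.5 SD imbalance, the change-score estimate shifts by (1 − r) × 0.5 = 0.35, 0.25, 0.15 and 0.05 SD at r = 0.3, 0.5, 0.7 and 0.9. The shift averages zero over trials, so this is imprecision and not bias.

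**5. Smoking stratum.** Suppose smoking shifts the change by g SD of change. With equal strata the pooled variance grows by a factor of about 1 + g²/4, while the treatment difference is no more variable because the strata are balanced. Simulated at r = 0.7:

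| g | t-test size | t-test power | ANCOVA size | ANCOVA power |
|---|---|---|---|---|
| 0 | 5.0% | 80% | 4.8–5.2% | 84–85% |
| 0.5 | 4.5% | 78% | same | same |
| 0.8 | 3.4% | 75% | same | same |
| 1.0 | 2.9% | 72% | same | same |

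The stratum can matter even at high r. If smoking shifts the follow-up value by 0.5 SD at r = 0.9, which is 0.5/√0.2 = 1.12 SD of change, power is 69% for the t-test and 80% for ANCOVA at a difference of 0.5 SD.

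**6. Skewed assays.** For log-normal data with the same effect on the log scale, and a decrease (the direction of MMP inhibition), the Wilcoxon test on raw change has power of about 57–66% at log SD 0.5 and 45–57% at log SD 1.0, over r = 0.3 to 0.95. The t-test on log change has about 80%, and log-scale ANCOVA about 93% falling to 80%. For an increase, the Wilcoxon loss is smaller or absent. At r of 0.9 or more the gain comes from the log scale and not from the covariate.

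**The case against.** The plan contains no error here. The planned tests hold their false-positive rate and are conservative if smoking predicts change. The aims are to characterise change in a pilot, and no power is claimed for any continuous endpoint; the 80% benchmark above is a reference point and not a target that the plan misses. All of that stands, and it is why the point is minor.

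The benefit also depends on r and on a smoking effect that the documents do not give. Of the three kinds of secondary endpoint in Section 7.1, doxycycline levels fall outside the point and FEV1 may gain nothing from baseline adjustment if its r is 0.9 or above. That leaves MMP activity as the main beneficiary among them, with the further BAL, serum and CAT measures in Section 6. This too stands. It limits the size of the gain but not its direction: over the assumed range the interval is between 18% narrower and 1% wider.

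The evidence is weaker for repeated endpoints. A mixed model was checked with two follow-up visits only, using a simple t reference. Serum is sampled at five follow-up visits (Weeks 2, 6, 12, 18 and 24), and that case was not tested. It is also unsettled which value is the baseline, because spirometry is done at both Screening and Entry, and whether spirometry occurs at Week 2, which the Section 7.2 text lists and Table I does not. These gaps qualify the mixed-model advice. They do not affect ANCOVA for endpoints with one follow-up, chiefly the BAL measures.

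**Conclusion.** The concern holds and is minor. For secondary endpoints with a meaningful baseline, the unadjusted comparison of change is valid but less efficient than ANCOVA on baseline and smoking stratum when r is below about 0.9. The interval could be about 6% to 18% narrower for r between 0.7 and 0.3, with 4 to 13 points more power where the t-test has 80%. At r of 0.9 or more, baseline adjustment gains nothing, and the stratum term helps only if smoking predicts change.

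These sizes rest on assumed correlations, equal variances over time, normal data (except in step 6) and complete follow-up. The arithmetic is firm; the gain in this trial cannot be known from the documents. The primary toxicity analysis does not change.

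**What to change.** Replace the unadjusted change-score comparison, for BAL MMP activity, cytokines and cell counts, serum markers, the CAT and spirometry, with ANCOVA of the follow-up value on treatment, baseline and smoking stratum. Leave doxycycline levels out. State which visit supplies the baseline and which follow-up visit is the target. List before unblinding the assays to be analysed on the log scale. Keep the Wilcoxon test on change as a sensitivity analysis.

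For endpoints with several follow-ups, prespecify one mixed model with the same two covariates and a small-sample degrees-of-freedom correction, for example Kenward-Roger. With two visits and 0%, 10% or 20% missing at the last, the false-positive rate was about 5.7%, 6.3% and 6.9% with a normal reference and 4.6–5.6% with a t reference. Kenward-Roger itself was not simulated, so check the chosen model at the real number of visits first.

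The cost is analysis wording and the choices just listed; no new data or subjects are needed. ANCOVA uses 26 degrees of freedom in place of 28. At r = 0.95 the interval is about 1% wider and power about 1 point lower.

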#### Exclusion Criteria:

- 1. Pulmonary infection, COPD exacerbation, or acute opportunistic infection within 30 days of entry
- 2. Conditions associated with increased sedation of bronchoscopy risk, including but not limited to Gold class 3 or 4 COPD, requirement for home oxygen, hypercapneic respiratory failure, poorly control hypertension
- 3. Known allergy/intolerance to doxycycline, atropine, or any local anesthetic
- 4. Inability to provide informed consent
- 5. Pregnant or lactating women
- 6. Men must agree not to attempt to make a woman pregnant of participate in sperm donation during the study and for 6 weeks after discontinuing the drug
- 7. End stage renal disease
- 8. Cirrhosis
- 9. INR greater than 1.4
- 10. Platelets less than 80,000
- 11. Any condition including active drug or alcohol use or dependence that, in the opinion of the site investigator, would interfere with adherence to study requirements or increase the risk of bronchoscopy
- 12. Active or planned participation in any other clinical trial or observational study without prior approval from the PI

**Endpoints:** The primary endpoint will be safety/tolerability, and secondary endpoints will include change in pulmonary function (FEV1) by spirometry, inhibition of MMP activity in a pan-MMP activity assay as well as individual MMPs assessed by gelatinase assays and doxycycline levels in serum, epithelial lining fluid and bronchoalveolar lavage cell pellets (consisting of alveolar macrophages, lymphocytes and some neutrophils).

**Statistical Considerations:** The overall sample size is 30 subjects, all of whom will be recruited at WCMC. We anticipate screening 70 subjects to randomize 30. The study investigates the safety/ tolerability (grade 2 or higher toxicity) of long-term use of doxycycline. A 20-30% rate of grade 2 or higher toxicity is expected. With 20 doxycycline recipients, we will have approximately 80% power (one-sided alpha = 0.05) to detect a true proportion of 20% (grade 2 or higher toxicity) while rejecting the null hypothesis of 45.5% or higher (in other words, ruling out the possibility of the event rate being any higher that 45.5%). Below are additional scenarios based on a true proportion of 5- 40% (P1), which demonstrate power greater than 80% for n = 20 doxycycline recipients under these assumptions.

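### Randomisation is stratified on smoking status, but the planned t-test and Wilcoxon comparisons do not use the stratum; if smoking predicts change, their intervals will be wider than needed

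*Combined protocol and SAP*

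**What the plan says.** In the Synopsis, Study Design, subjects are allocated "in a 2:1 fashion using permuted blocks of size 3 to receive doxycycline or placebo for 6 months", and "The randomization will be stratified on current versus former smoking status". On size, the Statistical Considerations say: "The overall sample size is 30 subjects, all of whom will be recruited at WCMC". At 2:1 that is about 20 doxycycline and 10 placebo subjects.

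The analysis methods appear in one place, the Statistical Considerations of the Synopsis:

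- Changes from baseline in continuous variables are compared "between the two groups by 2-sample t-tests or the non-parametric Wilcoxon's rank sum test as appropriate".
- For repeated measures: "We will perform repeated measures ANOVA or Multivariate ANOVA for repeated measures data (e.g. spirometry) as deemed appropriate". The model terms are not listed.
- Adverse-event proportions are "summarized by grade and compared by Chi-squared or Fisher's exact tests or generalized Fisher's test".
- One pre-specified subgroup analysis uses emphysema on CT, which is not the stratification factor.

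Smoking status is not named as a stratum, factor or covariate in any of these. The only power figure is a one-arm calculation for grade 2 or higher toxicity in doxycycline recipients.

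**The concern.** Permuted blocks of 3 within each smoking stratum hold the 2:1 ratio in both strata, apart from a possible incomplete last block. A difference between current and former smokers therefore largely cancels out of the treatment contrast. A two-sample t-test does not credit this: it leaves the between-stratum variance in the error term. When the stratum is prognostic, the standard error is overstated, the type I error falls below nominal and power is given up.

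This matters here because the placebo arm has about 10 subjects, the control group was included so that changes in biologic and physiologic endpoints could be interpreted, and the results are meant to inform a larger Phase II trial. Intervals that are wider than the design warrants would carry over into that planning.

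**Working it through.** **1. The plan's own power figure.** Inputs from the Statistical Considerations: n = 20 doxycycline recipients, null rate 45.5%, true rate 20%, one-sided alpha 0.05.

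- Exact binomial, rejecting with 5 or fewer events in 20: P(X ≤ 5 | 0.455) = 0.0505 and P(X ≤ 5 | 0.20) = 0.804.
- Normal approximation: Φ{[(0.455 − 0.20) − 1.645·√(0.455·0.545/20)] / √(0.20·0.80/20)} = Φ{(0.255 − 0.183)/0.0894} = Φ(0.80) = 0.789.

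The stated figure of about 80% reproduces. It concerns one arm and involves no between-arm test, so the stratum has no bearing on it. No power is stated for any lung-function or biologic endpoint.

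**2. Inputs for the between-arm check.** From the documents: 30 subjects, 2:1, blocks of 3, two strata. Assumed, because the documents give nothing: the share R² of the variance of the change score explained by smoking status, the split between current and former smokers, two-sided alpha 0.05, normal errors and no dropout. With a proportion p of current smokers and a difference of g within-stratum SDs between the strata, R² = p(1−p)g² / [1 + p(1−p)g²].

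**3. Width ratio by formula.** With exact 2:1 balance in each stratum, the residual sum of squares of the unadjusted t-test (28 df) has expectation 28σ² + 30·p(1−p)g²σ². The model with arm and stratum (27 df) estimates σ² itself. The ratio of 95% interval widths is therefore approximately

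(t₀.₉₇₅,₂₈ / t₀.₉₇₅,₂₇) · √[1 + (30/28)·R²/(1−R²)], where 2.0484/2.0518 = 0.998.

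At R² = 0.20: 0.998·√(1 + 1.071·0.25) = 0.998·1.126 = 1.124.

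**4. Formula and simulation side by side.** The simulations randomised in blocks of 3 within strata and compared the pooled t-test with a linear model on arm and stratum.

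| Assumed share R² | Difference g if p = 0.5 (SD) | Width ratio, formula | Width ratio, simulated | Type I error, unadjusted | Power lost (points) |
|---|---|---|---|---|---|
| 0% | 0 | 0.998 | 1.00 | 0.05 | 0 |
| 5% | 0.46 | 1.026 | 1.03 | 0.04 | about 1 |
| 10% | 0.67 | 1.056 | 1.06 | 0.04 | about 3 |
| 20% | 1.0 | 1.124 | 1.12–1.13 | 0.03 | 7–8 |
| 30% | 1.31 | 1.206 | 1.21 | 0.02 | 9–13 |

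The adjusted analysis keeps its type I error near 0.05 throughout. The range for power reflects how the treatment effect is scaled. With the effect fixed at 1.124 within-stratum SDs, which gives 80% power for a 20:10 t-test, power at g = 1.0 is 71.9% unadjusted and 79.3% adjusted, a loss of 7.4 points. With the effect scaled so that the unadjusted test stays near 80%, the pairs at 10%, 20% and 30% are 79% and 82%, 80% and 87%, and 82% and 91%.

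**5. Sensitivity to the smoking split.** With 70% current smokers, the width ratio is 1.00 at g = 0, 1.02 at 0.5 SD, 1.10 at 1.0 SD and 1.37 at 2.0 SD. With 50%, the corresponding values are 1.00, 1.03, 1.12 and 1.43.

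Nothing was computed for Wilcoxon against van Elteren, for the repeated-measures model, or for a stratified adverse-event test.

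**The case against.** The strongest reply is that nothing in the documents shows current versus former smoking to predict change from baseline. Change scores already remove stable smoking-related differences in level. The background on MMP response in HIV-infected smokers (Section 5.1) concerns levels, and the preliminary data (Section 5.3) report broad cytokine expression in HIV-positive individuals whether or not they smoke. Measuring nicotine metabolites, or stratifying on smoking, does not make it prognostic. This stands. A reader might infer that the intervals are certainly too wide and the error bars wrong; the documents support only the conditional statement. At shares of 0% to 5% the cost is nil to negligible, and a share of 20% to 30% requires current and former smokers to differ by 1.0 to 1.3 SD in change.

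A reader might also infer that every between-arm test ignores the stratum. That goes too far: the RM-ANOVA/MANOVA terms are not listed, so a smoking factor there is unstated, not excluded. Nor do the documents or the calculations support extending the point to adverse events. With about 10 placebo subjects divided over two strata, a gain from a stratified test has not been shown and is doubtful.

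Finally, these endpoints are secondary in a proof-of-concept pilot, and the error is in the conservative direction. That limits the importance of the point. It does not remove it, because the adjustment costs almost nothing when smoking is irrelevant (width ratio 0.997 in simulation at g = 0).

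**Conclusion.** The point holds in conditional form. The randomisation uses a smoking stratum that the planned t-test and Wilcoxon comparisons do not use and that is not named for the repeated-measures model. If smoking status predicts change, the unadjusted t-test is conservative: intervals about 3% wider than needed at an assumed 5% share of variance, 6% at 10%, 12% to 13% at 20% and 21% at 30%, with the power losses tabulated above. If smoking does not predict change, nothing is lost. These sizes rest on assumed variance shares, normal errors, two-sided alpha 0.05 and no dropout. They cannot be taken from the documents.

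It would be wrong to conclude that the tests are invalid, that the trial falls short of a planned power for lung-function or biologic endpoints (none is stated), or that the stated safety power is affected. This is an inexpensive gain in precision, not the repair of a faulty analysis.

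**What to change.** In the Statistical Considerations:

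- Replace the two-sample t-test on changes from baseline with a linear model containing arm and smoking stratum (current or former, as used at randomisation).
- Where a rank test is needed, use the van Elteren test stratified on smoking status in place of the plain Wilcoxon test.
- Name smoking stratum as a fixed effect in the repeated-measures model.
- Leave the chi-squared/Fisher comparison of adverse events as planned.

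The cost is wording and one degree of freedom (28 to 27 for the linear model). No new data are needed, since smoking status must be known to randomise. Naming the term in advance also avoids choosing a covariate after the data are seen.
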